9.3.4 CHANGE FROM BASELINE IN NUMBER OF MGYLS

The change from baseline to day 14, month 1, month 1.5, and month 3 in the number of Meibomian Glands Yielding Liquid Secretion (MGYLS) (0 to 15 scale) will be summarized using N, mean, standard deviation, median, minimum, and maximum.

An ANCOVA test will be performed to assess the difference of change from baseline in number of MGYLS between treatment groups with baseline MGYLS, baseline MGS score stratum and duration of disease stratum as covariates. The difference between treatment groups will be evaluated using t-tests

	TEMPLATE		
	DOCUMENT #:		TMP-191
	REVISION:		2.0
STATISTICAL ANALYSIS PLAN TEMPLATE	CC #:	836	PAGE 19 OF 25

of the least square means from this model. The two-sided confidence interval (95%) will be provided for the difference between treatments.

The following pseudocode will be used:

```
PROC GENMOD data=xxx;
BY visit;
CLASS treatment (ref = 'AZR-MD-001 VEHICLE') duration baseMGS;
MODEL chg =treatment base duration baseMGS;
LSMEANS treatment;
run;
```

9.3.5 MGYLS AT EACH VISIT

MGYLS (0 to 15 scale) at each visit will be summarized using N, mean, standard deviation, median, minimum, and maximum.

An ANCOVA test will be performed to assess the difference of MGYLS between treatment groups with baseline MGYLS, baseline MGS score stratum and duration of disease stratum as covariates. The difference between treatment groups will be evaluated using t-tests of the least square means from this model. The two-sided confidence interval (95%) will be provided for the difference between treatments.

The following pseudocode will be used:

```
PROC GENMOD data=xxx;
BY visit;
CLASS treatment (ref = 'AZR-MD-001 VEHICLE') duration baseMGS;
MODEL score =treatment base duration baseMGS;
LSMEANS treatment;
run;
```

9.3.6 CHANGE FROM BASELINE IN TBUT

The change from baseline to day 14, month 1, month 1.5, and month 3 in TBUT will be summarized and analyzed using the same methods as described in Section 9.3.4.

9.3.7 TBUT AT EACH VISIT

TBUT at each visit will be summarized and analyzed using the same methods as described in Section 9.3.5.

9.3.8 PROPORTION OF PATIENTS WITH TBUT > 5

	TEMPLATE		
	DOCUMENT #:		TMP-191
	REVISION:		2.0
STATISTICAL ANALYSIS PLAN TEMPLATE	CC #:	836	PAGE 20 OF 25

The proportion of patients with a TBUT score > 5 at each visit will be summarized and analyzed using the same methods as described in Section 9.3.3.

9.3.9 CHANGE FROM BASELINE IN SPEED

The change from baseline to day 14, month 1, month 1.5, and month 3 in SPEED will be summarized and analyzed using the same methods as described in Section 9.3.4.

9.3.10 SPEED AT EACH VISIT

SPEED at each visit will be summarized and analyzed using the same methods as described in Section 9.3.5.

9.3.11 PROPORTION OF PATIENTS WITH SPEED < 6

The proportion of patients with a SPEED < 6 at each visit will be summarized and analyzed using the same methods as described in Section 9.3.3.

9.3.12 CHANGE FROM BASELINE IN AVERAGE VAS

The change from baseline to day 14, month 1, month 1.5, and month 3 in average VAS will be summarized and analyzed using the same methods as described in Section 9.3.4.

9.3.13 AVERAGE VAS AT EACH VISIT

Average VAS at each visit will be summarized and analyzed using the same methods as described in section 9.3.5.

9.3.14 CHANGE FROM BASELINE IN WORST VAS

The change from baseline to day 14, month 1, month 1.5, and month 3 in worst VAS will be summarized and analyzed using the same methods as described in Section 9.3.4.

9.3.15 WORST VAS AT EACH VISIT

Worst VAS at each visit will be summarized will be summarized and analyzed using the same methods as described in section 9.3.5.

9.3.16 CHANGE FROM BASELINE IN TOTAL OSDI

The change from baseline to day 14, month 1 and month 1.5, in total OSDI will be summarized and analyzed using the same methods as described in Section 9.3.4.

9.3.17 OSDI ACROSS VISITS

	TEMPLATE		
	DOCUMENT #:		TMP-191
	REVISION:		2.0
STATISTICAL ANALYSIS PLAN TEMPLATE	CC #:	836	PAGE 21 OF 25

Total OSDI, OSDI sub-scales, and individual items from the OSDI across visits will be summarized and analyzed using the same methods as described in section 9.3.5.

9.3.18 PROPORTION OF PATIENTS WITH TOTAL OSDI CHANGE FROM BASELINE > 4.5 AT MONTH 3

The proportion of patients with a total OSDI change from baseline > 4.5, the known minimally important clinical difference (MICD) for early to moderate disease, at month 3 will be summarized and analyzed using the same methods as described in Section 9.3.3.

9.3.19 PROPORTION OF PATIENTS WITH TOTAL OSDI < 13

The proportion of patients with a total OSDI < 13 at each visit will be summarized and analyzed using the same methods as described in Section 9.3.3.

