## 1 PROTOCOL SUMMARY

### 1.1 SYNOPSIS

**Study Compound(s):** AZR-MD-001 (Selenium Disulfide)

---

**Phase:** 2b

---

**Objectives:** To evaluate the safety, tolerability and pharmacodynamics of AZR-MD-001 ointment/semi-solid drug applied to the lower lid twice-weekly for up to 3 months compared to its vehicle in patients with meibomian gland dysfunction (MGD).

**Clinical Hypotheses:** AZR-MD-001 ointment/semi-solid drug has an acceptable safety and tolerability profile following twice-weekly, evening peri-ocular administration for the study treatment duration.

AZR-MD-001 ointment/semi-solid drug is more effective than vehicle for treating MGD as measured by the meibum gland secretion score (MGS).

AZR-MD-001 ointment/semi-solid drug is more effective than vehicle for treating symptoms associated with MGD as measured by Total Ocular Surface Disease Index (OSDI) score.

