Eleven patients were randomized to Cohort 1, Group 1 (0.1%, twice-weekly) between September 10th, 2018 and October 19th, 2018 in ongoing clinical study AZ201801. Twelve patients were randomized to Cohort 1, Group 2 (0.5%, twice-weekly) between October 19th, 2018 and February 20th, 2019. Ten patients were randomized to Cohort 1, Group 3 (1.0%, twice-weekly) between April 22nd, 2019 and June 19th, 2019.

As specified in Protocol Amendment # 2 dated January 2019, the primary efficacy variables for MGD included change from baseline to month 3 in Meibomian Gland Score (MGS) and measures of Total Ocular Surface Disease Index (OSDI). Least Square (LS) mean changes from baseline (larger scores signal improvement) for MGS at month 3 were  $4.5 \pm 2.0$  ( $p = 0.025$ ) for the Vehicle Group;  $1.2 \pm 2.0$  ( $p = 0.56$ ) for the AZR-MD-001 0.1% Group (sub-therapeutic dose);  $4.9 \pm 2.1$  ( $p = 0.02$ ) for the AZR-MD-001 0.5% Group; and  $12.2 \pm 2.4$  ( $p < 0.0001$ ) for the AZR-MD-001 1.0% Group. Total OSDI showed the same pattern of results. Least square (LS) mean changes from baseline (smaller scores signal improvement) for Total OSDI at month 3 were  $0.0 \pm 3.4$  ( $p = 0.99$ ) for the Vehicle Group;  $9.5 \pm 3.8$  ( $p = 0.01$ ) for the AZR-MD-001 0.1% Group;  $-6.9 \pm 4.0$  ( $p = 0.08$ ) for the AZR-MD-001 0.5% Group; and  $-12 \pm 5.1$  ( $p < 0.01$ ) for the AZR-MD-001 1.0% Group. The difference of 12 between the Vehicle and AZR-MD-001 1.0% Groups was statistically significant ( $p = 0.03$ ) and the results appear dose responsive.

Based upon positive efficacy and safety results from clinical study MGSS1 for the ocular application of selenium disulfide shampoo (2.5%) and from Clinical Protocol AZ201801 for AZR-MD-001 (0.5% and 1.0%), Azura Ophthalmics is further evaluating the safety, tolerability and effectiveness of AZR-MD-001 (0.5%) ointment/semi-solid drug, surfactant free, in patients with MGD.

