### 9.4.3 ANALYSIS OF THE SECONDARY ENDPOINT(S)

The secondary efficacy variables (see Section 8.1.2) will be analyzed using an analysis of covariance [ANCOVA] model with baseline MGS score and duration of disease as covariates and treatment (AZR-MD-001 ointment/semi-solid drug or vehicle) as factors in the model. Pairwise comparisons will be performed for each AZR-MD-001 ointment/semi-solid drug treatment group versus vehicle using t-tests of the least square means from this model. Two-sided confidence intervals (95%) will be provided for the differences between treatments.

Descriptive statistics (change from baseline variables) will be tabulated for the following within treatment group changes in the mITT population:

- Patients in the AZR-MD-001 ointment/semi-solid drug treatment group: changes from baseline to days 14, month 1, month 1.5 and month 3
- Patients in the AZR-MD-001 vehicle group: changes from baseline to days 14, month 1, month 1.5 and month 3

Within each treatment group, shift tables for complete treatment response (yes/no) in the study eye will be presented for patients in the mITT population for endpoint signifying a “clinical cure” (Proportion of patients with a MGS score > 12; Proportion of patients with a MGYLS score of >2; Proportion of patients with a MGYLOS score of >2; Proportion of patients with a TBUT > 5 seconds at each visit; Proportion of patients with a Schirmer’s test  $\geq$  10 mm at each visit; Proportion of patients with a Total OSDI < 13 at each visit; and Proportion of patients with a SPEED Score < 6.

- Patients in the AZR-MD-001 ointment/semi-solid drug treatment group: changes from baseline to days 14, month 1, month 1.5 and month 3.
- Patients in the AZR-MD-001 vehicle group: changes from baseline to days 14, month 1, month 1.5 and month 3.

The Logistic Regression method for general association, stratified by baseline MGS score and duration of disease will be used to compare treatments with respect to the proportion of patients achieving a “clinical cure” in the study eye. Odds ratio along with 95% CI will be obtained by pairwise comparisons will be performed for each AZR-MD-001 treatment groups versus vehicle..

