## 14.2 OCULAR SURFACE DISEASE INDEX (OSDI)

The OSDI questionnaire consists of 12 questions regarding ocular symptoms, environmental triggers, and vision-related functioning in patients with DED. The patient will be asked to rate each symptom using a 5-point scale (0 to 4), where 0 = none of the time; 1 = some of the time; 2

= half of the time; 3 = most of the time; and 4 = all of the time. Seven questions related to visual functioning allow a response of "N/A" (not applicable). The total OSDI will be calculated by EDC from the raw scores of each of the 12 questions based on the formula:  $([\text{sum of scores for all questions answered}^a] \times 100) / ([\text{total number of questions answered}^a] \times 4)$ .

a Questions answered with N/A will be excluded in the calculation of total OSDI.

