	
(0 to 15 scale)
 
 • MGYLS (0 to 15 scale) at each visit • Change from Baseline to day 14, month 1, month 1.5, and month 3 in TBUT • TBUT at each visit • Proportion of patients with a TBUT score > 5 at each visit • Change from Baseline to day 14, month 1, month 1.5 and month 3 in Standard Patient Evaluation of Eye Dryness (SPEED) • SPEED at each visit • Proportion of patients with a SPEED < 6 at each visit • Change from Baseline to day 14, month 1, month 1.5 and month 3 in average visual analogue scale (VAS) • Average VAS at each visit • Change from Baseline to day 14, month 1, month 1.5 and month 3 in worst VAS • Worst VAS at each visit • Change from Baseline to day 14, month 1 and month 1.5 in Total OSDI • Total OSDI, OSDI sub-scales, and individual items from the OSDI across visits • Proportion of patients with a Total OSDI change from baseline > 4.5, the known minimally important clinical difference (MICD) for early to moderate disease, at month 3 • Proportion of patients with a Total OSDI < 13 at each visit • Number of expressible glands yielding clear meibum at day 14, month 1, month 1.5, and month 3 • Eyelid margin erythema/telangiectasias at day 14, month 1, month 1.5, and month 3 • Corneal and conjunctival staining (0 to 5 scale) at each visit 
Safety Endpoints:
 
 • Adverse events • Vital signs • Study medication tolerability as measured by the Ocular Comfort Questionnaire • Urine pregnancy test • Best-corrected visual acuity (BCVA; Logarithmic visual acuity chart) • Biomicroscopy
--	---

	TEMPLATE		
	DOCUMENT #:		TMP-191
	REVISION:		2.0
STATISTICAL ANALYSIS PLAN TEMPLATE	CC #:	836	PAGE 10 OF 25

	
 • Ophthalmoscopy • Intraocular pressure (IOP)
INTERIM ANALYSES	No interim analyses are planned for this study.
FINAL ANALYSES	All final planned analyses identified in this SAP will be completed after the last participant has completed 3-months follow up.

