4 SAMPLE SIZE

Estimates for sample size calculations are from the first interim analysis from Azura Clinical Protocol AZ201801. The standard deviation for MGS was 3.35 units for an ineffective dose and 9.48 units for the high dose. A sample size of 12 subjects per group will have 90% power to detect a difference of 10.4 units between the active treatment group and the vehicle group using a two-sample t-test at a significance level of 0.05. The standard deviation for Total OSDI was 13.01 units for an ineffective dose and 6.79 units for the high dose. A sample size of 11 subjects per group will have 90% power to detect a difference of 15.9 units between the active treatment group and the vehicle group using a two-sample t-test at a significance level of 0.05.

The total number of randomized patients for the study will be up to approximately 30. Approximately 15 patients should have a baseline MGS score of < 6 and approximately 15 patients should have a baseline

	TEMPLATE		
	DOCUMENT #:		TMP-191
	REVISION:		2.0
STATISTICAL ANALYSIS PLAN TEMPLATE	CC #:	836	PAGE 12 OF 25

MGS score ≥ 6 and ≤ 12 . Based upon data from ongoing study AZ201801 and the simplified inclusion/exclusion criteria for this study a screen failure rate of $\sim 40\%$ is expected. Thus, ~ 42 patients will need to be screened to achieve ~ 30 patients randomized to treatment.

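### The sign of change from baseline is never defined: under visit minus baseline, the OSDI rule (change > 4.5) counts worsening, and the BCVA table has no category for loss.

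*SAP*

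**What the plan says.** The OSDI rule appears in SAP 9.3.18 as "The proportion of patients with a total OSDI change from baseline > 4.5, the known minimally important clinical difference (MICD") at month 3. SAP 2 and 3.2.2, the protocol synopsis, protocol 8.1.2 and protocol 9.4.1 use essentially the same words (SAP 2: "Proportion of patients with a Total OSDI change from baseline > 4.5, the known minimally important clinical difference (MICD")). None of the six statements includes a word for decrease or improvement. The analysis follows SAP 9.3.3, a logistic regression whose code does not name the event level. The SAP's ANCOVA code uses a variable `chg` whose derivation is not given.

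The OSDI scale is clear. In protocol 14.2 items are scored "where 0 = none of the time; 1 = some of the time", rising to 4 for all of the time, so a higher total is worse.

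The intent is also clear. Protocol 1.1 hypothesises that the drug is "more effective than vehicle for treating symptoms associated with MGD as measured by Total Ocular Surface Disease Index (OSDI) score", and a companion responder endpoint in protocol 9.4.3 is "Proportion of patients with a Total OSDI < 13 at each visit".

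For BCVA, SAP 10.2 summarises letters read, where more is better. It classifies change from baseline as at most 5 or above 5, and as at most 10 or above 10, by eye and treatment group. There is no negative cut-point and no loss category.

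**The concern.** A one-sided cut-point on a change score means nothing until the sign of change is fixed. OSDI improves downwards and letters read improve upwards, yet both rules use a bare greater-than threshold. On the usual definition, visit minus baseline, a threshold above zero picks out worsening for OSDI and gain for BCVA. In each case the table would then miss the patients it is meant to count.

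At stake are the only MICD-based symptom endpoint, which could show worsening as response, and a vision safety table for a drug applied to the lid margin, which could not count patients losing more than 5 or 10 letters. If the direction is settled only after results are seen, the responder definition is open to choice by outcome.

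**Working it through.** No stated figure of the plan rests on this point, so the check compares passages and applies the sign logic.

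**Step 1. Which convention do the documents fit?** Protocol 2.2 gives signed month 3 results from the earlier study. MGS changes are 4.5 (vehicle), 1.2 (0.1%), 4.9 (0.5%) and 12.2 (1.0%), with larger values described as better. For OSDI the text gives "mean changes from baseline (smaller scores signal improvement) for Total OSDI at month 3": 0.0 (vehicle), 9.5 (0.1%), -6.9 (0.5%) and -12 (1.0%). MGS rises with benefit: a score of 12 or less is required for entry, and above 12 counts as clinical cure in protocol 9.4.3. OSDI falls with benefit.

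- Visit minus baseline: MGS improvement is positive and OSDI improvement is negative. Both match.
- Baseline minus visit: MGS improvement would be negative and OSDI improvement positive. Neither matches.

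The requirement in SAP 7.5 that MGS be significantly higher on active is also consistent with visit minus baseline. Against that, SAP 7.3 speaks of a reduction in MGS, a score where higher is better, so direction wording is not controlled within the SAP.

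**Step 2. Apply the OSDI rule (change > 4.5).** Take hypothetical patients whose change equals the group means above:

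| Visit minus baseline | Patient has | Counted, visit minus baseline | Counted, unsigned | Counted, baseline minus visit |
|---|---|---|---|---|
| -12 | improved | no | yes | yes |
| -6.9 | improved | no | yes | yes |
| 0.0 | not changed | no | no | no |
| +9.5 | worsened | yes | yes | no |

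**Step 3. Apply the BCVA splits.** Illustrative changes in letters (negative is loss):

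| Letters | Visit minus baseline | Unsigned | Baseline minus visit |
|---|---|---|---|
| -15 | <= 5, <= 10 | > 5, > 10 | > 5, > 10 |
| -8 | <= 5, <= 10 | > 5, <= 10 | > 5, <= 10 |
| 0 | <= 5, <= 10 | <= 5, <= 10 | <= 5, <= 10 |
| +8 | > 5, <= 10 | > 5, <= 10 | <= 5, <= 10 |
| +12 | > 5, > 10 | > 5, > 10 | <= 5, <= 10 |

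On visit minus baseline, a 15-letter loss shares both categories with no change. Unsigned, an 8-letter loss and an 8-letter gain are indistinguishable. Only baseline minus visit isolates losses.

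**Step 4. Are the primary analyses touched?** No. They compare mean change with two-sided tests and use no responder cut-point. The sample size depends on the size of the difference, not its sign. For OSDI, SDs of 13.01 and 6.79, a difference of 15.9, 11 per group and two-sided 0.05 (unequal-variance t-test) give power 0.919. For MGS, SDs of 3.35 and 9.48, a difference of 10.4 and 12 per group give 0.914. Both stated sample sizes reproduce.

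**Step 5. Can a size be put on the OSDI reversal?** Not usefully. It would need a group SD for 0.5%, which the documents do not give. Multiplying the ± values in protocol 2.2 by the square root of the number randomized does not reliably recover the SDs in SAP 4 ("The standard deviation for Total OSDI was 13.01 units for an ineffective dose and 6.79 units for the high dose"), if the ineffective dose is assumed to be 0.1% and the high dose 1.0%:

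- OSDI 0.1%: 3.8 × √11 = 12.6, stated 13.01.
- OSDI 1.0%: 5.1 × √10 = 16.1, stated 6.79.
- MGS 0.1%: 2.0 × √11 = 6.6, stated 3.35.
- MGS 1.0%: 2.4 × √10 = 7.6, stated 9.48.

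Three of the four disagree. The conclusion does not need a figure.

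**The case against.** The strongest reply is that nothing is proven wrong. If change is taken as baseline minus visit, OSDI above 4.5 is improvement, BCVA above 5 or 10 letters is loss, and both rules do what was intended. Protocol 2.2 reports an earlier study and does not define this trial's variables, and no signed BCVA result appears anywhere. The MICD label and the hypothesis make the intent so plain that a programmer would probably code improvement, and an inverted OSDI table would visibly clash with the primary OSDI result.

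Much of this stands. It limits the point to a missing definition with unsigned cut-points. A reader might infer that the SAP will report worsening as response, or that losses of vision will go unseen. The documents support neither without the condition that change is visit minus baseline.

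The BCVA gap is also partly covered. SAP 10.2 tabulates the minimum change by eye, arm and visit. Protocol 9.4.8 provides individual listings. Protocol 8.3.1 has patients asked about new or changed symptoms, so a loss that the patient notices can be recorded as an adverse event. None of these gives the number of patients beyond a stated loss in each arm, although that number could be counted by hand from the listings.

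The reply does not remove the defect. The harmless reading is the one that contradicts the only signed results in the documents, and evident intent does not make a written rule say what was meant.

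**Conclusion.** The point holds in conditional form. Change has no defined sign. On visit minus baseline, the convention that fits protocol 2.2, the OSDI rule as worded selects patients who worsened by more than the MICD, and the BCVA table separates gains while merging all losses with no change. Unsigned, both mix the two directions. Only baseline minus visit makes both work.

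The reach is small: one non-primary endpoint, whose comparisons SAP 7.5 calls descriptive, and one safety table. The stronger inference that the primary symptom result, the power or the error rate is at risk is not supported. The conclusion assumes only the scale directions stated in the documents (a higher OSDI is worse, more letters read is better). It should still be corrected before results are seen, because the apparent direction of the responder result depends on it.

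**What to change.** In the SAP:

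1. Define change from baseline once, as the visit value minus the baseline value.
2. In 9.3.18, 2 and 3.2.2, state the OSDI responder as a decrease in Total OSDI of more than 4.5 (change < -4.5), and name that response as the modelled event in the logistic regression.
3. In 10.2, tabulate losses of more than 5 and more than 10 letters by eye and treatment group, with gains shown separately.

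Align the protocol synopsis, 8.1.2 and 9.4.1 at the next amendment. Amendments need ethics approval under protocol 10.1, and this wording alone does not warrant one.

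The cost is low: a few lines of SAP text and one revised table layout, with no new data and no change to the primary analyses.

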9.3.20 NUMBER OF EXPRESSIBLE GLANDS YIELDING CLEAR MEIBUM

The number of expressible glands yielding clear meibum at day 14, month 1, month 1.5, and month 3 will be summarized and analyzed using the same methods as described in section 9.3.5.

9.3.21 EYELID MARGIN ERYTHEMA AND TELANGIECTASIAS

Eyelid margin erythema and telangiectasias scores at day 14, month 1, month 1.5, and month 3 will be summarized using N, mean, standard deviation, median, minimum, and maximum. Actual values and shifts from baseline will be summarized by parameter and time point. Changes from baseline will be analyzed at each time point using Cochran-Mantel-Haenszel (CMH) statistics to test for a treatment effect.

The following pseudocode will be used:

```
PROC FREQ data=xxx;
BY visit;
TABLE treatment * base * result / CMH;
ODS output CMH=outcmh (where=(ALTHYPOTHESIS='General Association'));
run;
```

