- Unwilling to abstain from the use of systemic or topical treatments for MGD or dry eye for the study duration (Including over-the-counter [OTC] artificial tears, ocular lubricants, or dietary supplements known to impact ocular surface health)
- Eyelid abnormalities that affect normal lid function in either eye other than those caused by meibomian gland dysfunction
- Diagnosis of hepatitis C infection, human immunodeficiency virus (HIV) infection, sarcoidosis, amyloidosis, active tuberculosis, or graft versus host disease
- History of anterior segment surgery or trauma that could affect corneal sensitivity (e.g., cataract surgery or any surgery involving a limbal or corneal incision) in either eye within the 12 months prior to the screening visit

- Planned anterior segment surgery (e.g., cataract surgery or any surgery involving a limbal or corneal incision) in either eye during the study period
- Meibography score at the screening visit of 4 (greater than 75% partial glands using the gestalt grading system)
- Corneal staining  $\geq 3$  (between 33 and 100 dots) using the Oxford Scheme
- Schirmer's tear test without anesthesia  $\leq 5$  mm in either eye at the baseline visit
- Known allergy or sensitivity to fluorescein, lissamine green, or the study medication or its components
- Use of medicated shampoos containing selenium (e.g., Selsun Blue, Exsel, Selsum, and Seleen) following the screening visit
- Patient is unlikely to follow study instructions or to complete all required study visits or has a condition or situation that in the investigator's opinion, may put the patient at significant risk, may confound the study results, or may interfere significantly with the patient's participation in the study
- Patient is an employee at the investigational site or is related to any member of the study staff
- Pregnant, nursing, or females of childbearing potential and not utilizing adequate birth control measures. Woman of childbearing potential may have a monogamous partner who has had a vasectomy at least 3 months before the screening visit or who is of the same gender.
- Positive urine pregnancy test at the screening visit
- Participation in another clinical trial involving a therapeutic drug or device within the past 30 days

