### 9.4 STATISTICAL ANALYSES

#### 9.4.1 GENERAL APPROACH

In general, continuous data will be summarized with descriptive statistics (number of patients, mean, standard deviation, median, minimum, and maximum) and will be analyzed using analysis of variance (ANOVA) techniques or 2-sample t-tests for between-group comparisons, and paired t-tests for within-group analyses. Categorical variables will be summarized by sample size (N), frequency count, and percent, and they will be analyzed using Pearson's chi-square test or Fisher's exact test (if the expected cell count is less than 5 in 25% or more of the cells). Ordinal variables will be analyzed using the Wilcoxon rank-sum test for between-treatment comparisons and the sign-rank test for within-treatment comparisons.

*Efficacy (MGD):*

*Primary Sign for MGD:*

- Change from Baseline to month 3 in meibum gland secretion score (MGS) (0 to 45 scale)

*Primary Symptom for MGD:*

- Change from Baseline to month 3 in Total OSDI

*Other Efficacy Measures:*

- Change from Baseline to day14, month 1 and month 1.5 in MGS (0 to 45 scale)
- MGS score (0 to 45 scale) at each visit
- Proportion of patients with a MGS score > 12 at each visit
- Change from Baseline to day14, month 1, month 1.5 and month 3 in the number of Meibomian Glands Yielding Liquid Secretion (MGYLS) (0 to 15 scale)
- MGYLS (0 to 15 scale) at each visit
- Change from Baseline to day 14, month 1, month 1.5, and month 3 in TBUT
- TBUT at each visit
- Proportion of patients with a TBUT score > 5 at each visit
- Change from Baseline to day 14, month 1, month 1.5 and month 3 in Standard Patient Evaluation of Eye Dryness (SPEED)
- SPEED at each visit
- Proportion of patients with a SPEED < 6 at each visit
- Change from Baseline to day 14, month 1, month 1.5 and month 3 in average visual analogue scale (VAS)
- Average VAS at each visit
- Change from Baseline to day 14, month 1, month 1.5 and month 3 in worst VAS
- Worst VAS at each visit
- Change from Baseline to day 14, month 1 and month 1.5 in Total OSDI
- Total OSDI, OSDI sub-scales, and individual items from the OSDI across visits
- Proportion of patients with a Total OSDI change from baseline > 4.5, the known minimally important clinical difference (MICD) for early to moderate disease, at month 3
- Proportion of patients with a Total OSDI < 13 at each visit
- Number of expressible glands yielding clear meibum at day14, month 1, month 1.5, and month 3

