9.3.22 CORNEAL AND CONJUNCTIVAL STAINING AT EACH VISIT

Corneal and conjunctival staining scores (0 to 5 scale) at each visit will be summarized by frequency of each score and shift from baseline. Changes from baseline will be analyzed at each time point using Cochran-Mantel-Haenszel (CMH) statistics as described in section 9.3.21.

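### The CMH code in SAP 9.3.21, reused in 9.3.22, does not compare treatments as written, and once reordered it would still ignore the order of the grades

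*SAP*

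**What the plan says.** SAP 9.3.21 analyses changes from baseline at each time point "using Cochran-Mantel-Haenszel (CMH) statistics to test for a treatment effect". Its pseudocode requests "TABLE treatment * base * result / CMH" and then filters the output with "ODS output CMH=outcmh (where=(ALTHYPOTHESIS='General Association".

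SAP 9.3.22 covers "Corneal and conjunctival staining scores (0 to 5 scale) at each visit" and repeats the method by reference: "Changes from baseline will be analyzed at each time point using Cochran-Mantel-Haenszel (CMH) statistics as described in section 9.3.21".

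On ordered data in general, the documents give more than one rule:

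- Protocol 9.4.1: "Ordinal variables will be analyzed using the Wilcoxon rank-sum test for between-treatment comparisons".
- Protocol synopsis, Protocol 9.4.5 and SAP 8: either CMH or the Wilcoxon rank-sum test, with no CMH statistic named.
- Protocol 9.4.3: ANCOVA for the secondary variables of Protocol 8.1.2, a list that includes both lid-margin signs and staining.

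SAP 13 lists one change from the protocol, the removal of pairwise-comparison wording. It says nothing about how these grades are tested. SAP 7.5 describes comparisons on the other efficacy endpoints as descriptive and leaves them unadjusted for multiplicity.

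**The concern.** In a three-way PROC FREQ request the last two variables form the table and the first is the stratum. The coded request therefore cross-classifies baseline grade with follow-up grade separately in each arm. Patients who start with a worse grade tend to finish with a worse grade, so this test can give a small p-value when the drug does nothing. SAP 9.3.21 would report that p-value as a treatment effect.

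The second fault remains after the variables are reordered. General Association uses no scores: relabel the grades in any order and the p-value is unchanged. A fall from grade 3 to 0 counts no more than a fall from 3 to 2, and on a six-grade scale the test spends up to 5 degrees of freedom where an ordered test spends 1.

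These are the only between-arm tests the SAP plans for staining and lid-margin signs; biomicroscopy (SAP 10.3) has frequencies and shift tables only. A consistent shift in staining matters in either direction, since Protocol 6.4.1 foresees worsening keratitis.

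**Working it through.** **Inputs from the documents.** About 30 patients randomised 1:1, so about 15 per arm (SAP 4; Protocol 4.1). Staining has six ordered grades, 0 to 5. Corneal staining of grade 3 or more, "between 33 and 100 dots) using the Oxford Scheme", is excluded (Protocol 5.2), so baseline corneal grades run from 0 to 2. The documents state no power figure for these endpoints, so there is none to reproduce. They also give no grade distribution, effect size or lid-margin grading scale, and everything on power below rests on assumed values.

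**Step 1: what the coded test measures.** General Association has (R−1)(C−1) degrees of freedom, where R and C count table rows and columns.

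- As coded, for corneal staining: rows are baseline (3), columns are result (6), strata are the two arms; up to 2 × 5 = 10 df.
- With treatment as the row: 1 × 5 = 5 df for General Association, and R−1 = 1 df for Row Mean Scores.

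A constructed example shows the effect. Put 15 patients in each arm, five at each of baseline grades 0, 1 and 2, and let nobody change. The arms are identical. Within an arm the Pearson statistic is 15 × (3−1) = 30, and the one-stratum CMH value is (14/15) × 30 = 28. Two identical strata add to 56 on 4 df, and p = e^(−28) × (1 + 28) ≈ 2 × 10^(−11). Swapping only the filter does not help. Row Mean Scores on the coded table is 14 + 14 = 28 on 2 df, p = e^(−14) ≈ 8 × 10^(−7). With baseline as the stratum, all ten patients at each grade have the same result, so there is no evidence of a treatment difference.

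Less extreme data were simulated with latent-normal grades, 15 per arm and no drug effect, at 1,500 trials per setting (standard error of a power about 1.3 points). At baseline-to-result correlation 0.5 the coded test rejects in about 13% to 34% of trials over 3 to 6 grades. With 4 and 5 grades it rejects in 51% to 62% at correlation 0.7 and 90% to 96% at 0.85. The rate does not rise with a treatment effect: for 5 grades at correlation 0.5 it is 18.5% at no shift and 14.9% at a shift of 1.0 SD.

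**Step 2: the cost of ignoring order, with the table corrected.** All figures are for 15 per arm, stratified by baseline grade, two-sided 0.05, corneal staining with baseline 0 to 2 and result 0 to 5.

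| Assumed effect | General Association | Row Mean Scores | Loss (points) |
|---|---|---|---|
| Odds ratio 3 | 12% | 32% | 20 |
| Odds ratio 5 | 27% | 58% | 31 |
| Odds ratio 8 | 46% | 77% | 31 |
| Shift 0.8 SD | 26% | 52% | 25 |
| Shift 1.0 SD | 40% | 70% | 30 |
| Shift 1.2 SD | 54% | 83% | 29 |
| Shift 1.5 SD | 73% | 94% | 21 |

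The odds-ratio rows use a proportional-odds model with a baseline slope of 1.2 on the logit scale. The shift rows use latent-normal grades with correlation 0.5; their losses are taken before rounding. A second proportional-odds simulation gave 12% vs 31%, 25% vs 56% and 42% vs 76%, losses of 19, 31 and 34 points. At a shift of 0.5 SD both tests are weak, 10% vs 24%.

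Varying the scale from 3 to 6 grades, the arm from 12 to 15 patients and the shift from 0.8 to 1.5 SD gives losses from about 8 points (3 grades, 15 per arm, 1.5 SD) to 46 points (6 grades, 12 per arm, 1.2 SD).

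**Step 3: large-sample check.** At noncentrality (1.96 + 0.84)² ≈ 7.85, power is 80% on 1 df and 70.9%, 64.5%, 59.5% and 55.5% on 2, 3, 4 and 5 df. The extra degrees of freedom alone explain much of the loss.

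**The case against.** **The power figures do not describe the test as written.** This is correct. A reader might infer that the planned test loses a fixed number of points of power, or that it is conservative. Neither follows, because the coded test does not compare arms and its larger risk is a spuriously small p-value. The power loss, and null rejection below 5% (3.1% against 5.5% for the ordered test in the latent-normal corneal case), belong to General Association only after the variables are reordered.

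**CMH is a method the protocol names.** Also correct. Protocol 9.4.1 read alone suggests that the SAP departed from the protocol by using CMH. The synopsis, Protocol 9.4.5 and SAP 8 allow CMH or Wilcoxon, so that reading is not supported. None of them selects General Association, though, and permission to use CMH does not make a nominal statistic suitable for ordered grades.

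**The size is assumed.** It is. Without a stated grade distribution or effect, only a range can be given. The direction does not depend on the model: every simulated shift of 0.8 SD or more favoured the ordered test.

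**The endpoints are descriptive.** SAP 7.5 says so, and shift summaries would show the direction whatever p-value is printed. This limits the importance of the point. It does not justify printing, at every visit, a p-value that answers a different question.

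**Conclusion.** Both faults stand and should be corrected together. As written, the code yields a p-value for the association of baseline with follow-up grade within arms, against the SAP's stated purpose; this follows from the table request and needs no assumptions. Once treatment is made the row variable, keeping only General Association would cost roughly 20 to 35 points of power for a moderate to large monotone shift in staining grade at 15 per arm, and about 8 to 46 points across wider assumptions. Those sizes depend on assumed distributions and effects.

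The consequence is confined to lid-margin signs and staining. The MGS and OSDI tests and their hierarchy do not use this code, so no primary conclusion is at risk.

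**What to change.** In SAP 9.3.21, and through it 9.3.22, replace the table request with `TABLE base*treatment*result / CMH SCORES=MODRIDIT` and keep the row where `ALTHYPOTHESIS='Row Mean Scores Differ'`. State in the text that this is the stratified Wilcoxon (van Elteren) test with baseline grade as the stratum. Within a baseline grade, ranking results and ranking changes are the same thing, so it still answers the change-from-baseline question. General Association can stay as a supplement at most.

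The choice agrees with the rank test in Protocol 9.4.1 and with the CMH-or-Wilcoxon wording elsewhere. Add an entry to SAP 13 reconciling it with the ANCOVA rule in Protocol 9.4.3.

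The cost is two code edits (table request and filter), a sentence of text and the SAP 13 entry, with no new data or software. The ordered test is less sensitive to non-monotone differences, such as one arm being more spread out around the same average grade. A baseline grade found in only one arm contributes nothing to the comparison, but that is equally true of General Association in the corrected layout.
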